4.2.6.3 Change of eosinophils by visit

Summary statistics of the change and percent change from baseline in blood eosinophil counts will be provided for all post-baseline visit by treatment group.

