1.2 Rationale for conducting this study

The treatment options for patients who remain uncontrolled by ICS-LABA are extremely limited.

In previous clinical studies, benralizumab administration resulted in rapid and prolonged depletion of eosinophils in the peripheral blood and in the asthmatic airway with associated improvements in multiple metrics of asthma control. The purpose of this study is to continue to characterize the safety profile of benralizumab administration in asthma patients who have completed 1 of the 3 predecessor studies: D3250C00017, D3250C00018, or D3250C00020.

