5.2.5 Safety laboratory tests

Safety laboratory tests (list provided in [Table 3](#) and [Table 4](#)) will be performed in a central laboratory. For information on methods of collection, assessment, labelling, storage and shipment of samples, please refer to the separate Laboratory Manual. Safety samples will be collected in accordance with the schedules provided in [Table 1](#) or [Table 2](#).

Hematology and urinalysis will be assessed in line with the schedules provided in [Table 1](#) or [Table 2](#). A detailed schedule of the chemistry tests is presented in [Table 3](#) and [Table 4](#). Visit 1 of this study is to be combined with the EOT visit of the predecessor study (see [Section 4.1.1](#)), therefore safety laboratory tests performed at the EOT visit in the predecessor study will be considered as baseline for this safety extension study. NB: As the required list of safety laboratory tests at Visit 1 of this safety extension study differs from those collected at EOT of the predecessor studies, the additional parameters required for this study (ie, those not required at the EOT visit of the predecessor study) will only be reported in this study to avoid duplicate reporting. Refer to the separate Laboratory Manual for more details.

Laboratory results should be reviewed by the Investigator/authorized delegate and evaluated for abnormalities. Any laboratory abnormalities considered significant in the Investigators'/authorized delegate's judgement should be reported as described to in [Section 7.1.3](#).

The copy of the laboratory results report should be signed and date by Investigator and retained at the study center.

Table 3 List of safety laboratory tests

Serum chemistry		Hematology	Urinalysis
Alkaline phosphatase	Gamma-GT (gamma-glutamyl transpeptidase)	Hematocrit	Appearance
ALT (alanine aminotransferase)	Glucose	Hemoglobin	Blood
AST (aspartate aminotransferase)	Phosphorus	Mean corpuscular volume (MCV)	Colour
BUN (blood urea nitrogen)	Potassium	Platelet count	Glucose
Calcium	Sodium	Red blood cell (RBC) count	Ketones
Chloride	Total bilirubin	WBC count with differential ^a	Microscopy including WBC/high power field (HPF), RBC/HPF
CO ₂ (carbon dioxide)	Total cholesterol		pH
Creatinine	Uric acid		Specific gravity
Serum concentration ^b			

^a Eosinophil, basophil and monocyte counts will be redacted from the central laboratory reports

^b For patients who are on theophylline or digoxin (see Section 3.5.2.2)

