| 
 1. To assess the impact of 2 dosing regimens of benralizumab on blood eosinophil levels for adult patients during the 56-week treatment period and through follow-up period (16 weeks from day of last dose) 2. To assess the impact of 2 dosing regimens of benralizumab on blood eosinophil levels for adolescent patients during the 108-week treatment period and through the follow-up period (16 weeks from day of last dose) | 
 • Blood eosinophils |

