2.4 Baseline and change from baseline

In general, the last non-missing value on or prior to the first dose of IP in BORA will be used as the baseline. The last evaluable post-dose record from the predecessor studies will also be

considered in the selection of baseline value for BORA study. If there is no assessment present, then the baseline value will not be imputed and will be set as missing. Exceptions for both pre-bronchodilator (pre-BD) and post-bronchodilator (post-BD) FEV₁ as specified below.

For pre-BD FEV₁, the following hierarchy rules will be applied to derive baseline:

- Step 1: Select values with acceptable quality (acceptable or borderline quality grade) on the same date closest to the first IP dose in BORA. If the assessments are on the same day of the first IP dose, only the assessments on or prior to the IP dose are used.
- Step 2: If there are central and local spirometry assessments on the same day, central spirometry assessments will be used.
- Step 3: If there are multiple assessments with different times, the earliest assessment will be used.
- Step 4: If there are multiple assessments with the same date and time, the value recorded in the BORA study database will be used.

For post-BD FEV₁, the baseline will be derived independently from pre-BD FEV₁ assessments. With exception from Step 2 to select the highest value within central or local spirometry, the same hierarchy rules as explained above will be applied.

Change from baseline will be calculated as the post-baseline assessment value minus the baseline assessment value. If either value is missing, then the change from baseline value will be missing.

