3.1.2 Laboratory variables

Blood and urine samples for determination of clinical chemistry, haematology and urinalysis parameters will be taken at times detailed in the CSP, and will be assessed in a central laboratory. The parameters outlined in Section 5.2.5, Tables 3 and 4 of the CSP will be collected. Laboratory data is to be reported in SI units. Eosinophils data will be presented in both SI and conventional units (cells/ μ L) in summaries.

Changes in haematology and clinical chemistry variables between baseline and each subsequent assessment will be calculated. For values recorded with a leading greater than or less than ('>', '<') symbol, the reported numeric value will be used for analysis and the value

with the symbol will be included in the listings, unless otherwise specified. For example, a value of <0.01 will be analysed as 0.01 and listed as <0.01.

Absolute values will be compared to the relevant reference range and classified as low (below range), normal (within range or on limits) or high (above range). The central laboratory ranges will be used for laboratory variables. All absolute values falling outside the reference ranges will be flagged.

Urinalysis data will be categorised as negative (0), positive (+), or strongly positive (++, +++, or >+++) at each time-point.

For the purposes of haematology, clinical chemistry and urinalysis shift tables, baseline will be defined as the latest non-missing assessment prior to first IP dose date, and maximum or minimum value post-baseline will be calculated over the entire post-baseline period, including the post-treatment unscheduled assessments.

For the liver function tests: Aspartate Aminotransferase (AST), Alanine Aminotransferase (ALT), Alkaline phosphatase, Gamma-GT (GGT) and total bilirubin (TBL), the multiple of the central laboratory upper limit of the normal (ULN) range will be calculated for each data point.

$$\text{Multiple} = \text{Value} / \text{ULN}$$

For example, if the ALT value was 72 IU/L (ULN 36) then the multiple would be 2.

Patients who meet any of the following criteria at any point during the study will be flagged:

- AST $\geq 3 \times$ ULN
- ALT $\geq 3 \times$ ULN
- TBL $\geq 2 \times$ ULN

In addition to the safety laboratory tests, immunoglobulins and T cell, B cell and NK cell (TBNK) flow cytometry are collected for adolescent patients.

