4.2.6 Analysis methods for efficacy variables

All efficacy data from SIROCCO and CALIMA will be summarized by treatment for the patients with predecessor baseline blood eosinophil count $\geq 300/\mu\text{L}$ and $< 300/\mu\text{L}$. Efficacy data from ZONDA will be summarised for the FAS regardless of predecessor baseline eosinophil counts.

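### In patients continuing benralizumab, eosinophil percent change is taken from an on-treatment count, so it is unstable and does not measure depletion from the pre-benralizumab level

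*SAP*

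**What the plan says.** The eosinophil section of the SAP (4.2.6.3) reads: "Summary statistics of the change and percent change from baseline in blood eosinophil counts will be provided for all post-baseline visit by treatment group". It defines no baseline of its own, so the rule in SAP 2.4 applies: "In general, the last non-missing value on or prior to the first dose of IP in BORA will be used as the baseline". The only exceptions listed there are pre- and post-bronchodilator FEV₁. Protocol 5.2.5 agrees: "safety laboratory tests performed at the EOT visit in the predecessor study will be considered as baseline for this safety extension study". Protocol 4.1.1 puts that visit on the same day as BORA Visit 1, so that dosing is not interrupted.

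Other places that bear on the point:

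- Protocol 1.2, on previous studies: "benralizumab administration resulted in rapid and prolonged depletion of eosinophils in the peripheral blood".
- SAP 1.1, the objective: "To assess the impact of 2 dosing regimens of benralizumab on blood eosinophil levels for adult patients during the 56-week treatment period". It continues through follow-up and has a parallel objective for adolescents. The endpoint is blood eosinophils.
- SAP 4.1 presents four groups: each BORA regimen, divided by predecessor treatment (the same benralizumab regimen, or placebo).
- SAP 3.1.2, on results reported with a less-than sign: "a value of <0.01 will be analysed as 0.01 and listed as <0.01". No rule covers a recorded 0 as a denominator.
- SAP 4.2.6 splits SIROCCO and CALIMA data into "patients with predecessor baseline blood eosinophil count" at or above, and below, 300/µL. The predecessor baseline count is therefore in use as a grouping variable, but not as a reference for change.
- SAP 4.2.5.2 summarises laboratory parameters by visit as absolute values and changes from baseline, and names eosinophils. SAP 4.2.10 adds counts by visit and median profiles by anti-drug antibody status.

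**The concern.** Percent change is informative when the denominator is a pre-treatment level. In the two continuing groups the denominator already contains the predecessor treatment effect. A patient who stays almost fully depleted can show a large increase, a decrease or no value at all, depending on a difference of a few cells. Recovery after the last dose is expressed as a multiple of a very small number instead of as a fraction of the level before benralizumab.

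The predecessor-placebo columns beside them report true depletion under the same label. A reader of the clinical study report could compare the four columns as if they measured one quantity, on a named secondary objective.

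The documents make this distinction elsewhere. Protocol 8.5.1.4 describes Visit 1 as pre-treatment only for patients not previously randomised to benralizumab, and gives the others a maintenance outcome. SAP 4.2.6.1 limits time to first exacerbation to predecessor-placebo patients. The eosinophil section has no such distinction.

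**Working it through.** The plan states no eosinophil count, target or power for this endpoint, so there is no figure of its own to reproduce.

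**Step 1: the baseline each group receives** (SAP 2.4 and 4.1; protocol 4.1.1 and 5.2.5)

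| BORA regimen | Predecessor arm | Entry count taken | Percent change from it measures |
|---|---|---|---|
| Q4W | Q4W | on benralizumab | variation around the depleted level |
| Q8W | Q8W | on benralizumab | variation around the depleted level |
| Q4W | placebo | before any benralizumab | depletion |
| Q8W | placebo | before any benralizumab | depletion |

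Protocol 6.6 keeps site staff blind to eosinophil results up to Visit 2 to protect the predecessor blind. That fits the view that counts around BORA entry differ visibly by predecessor arm.

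**Step 2: one patient.** Change = later − baseline; percent change = 100 × (later − baseline) / baseline. Assumed counts in cells/µL, not from the documents: 400 before benralizumab, 10 at BORA entry, 20 at Week 56, 200 at Week 68.

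| Visit | Percent change from entry (as planned) | Percent change from predecessor baseline | Absolute change from entry |
|---|---|---|---|
| Week 56 | (20−10)/10 = +100% | (20−400)/400 = −95% | +10 |
| Week 68 | (200−10)/10 = +1900% | (200−400)/400 = −50% | +190 |

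With an entry count of 0, neither percentage in the planned column exists, while absolute change still does.

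**Step 3: a group with no true change.** Simulation of 200,000 patients. Assumptions: counts recorded in steps of 10 cells/µL; entry and later counts independent, each 10 × a Poisson variable with the same mean.

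| Assumed mean count | Entry 0, percent change undefined | Percent change in the rest: mean (SD); median | Zeros reported as <10 and analysed as 10: mean (SD) | Absolute change: mean (SD) |
|---|---|---|---|---|
| 5 | 60.8% | −56 (66); −100 | +6 (39) | 0.0 (10.0) |
| 10 | 36.7% | −23 (86); −50 | +17 (71) | 0.0 (14.1) |
| 20 | 13.5% | +15 (110); 0 | +35 (111) | 0.0 (20.0) |
| 30 | 4.9% | +30 (120); 0 | +40 (127) | −0.1 (24.5) |

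Two columns can be checked by hand. The undefined share is exp(−mean/10) = 0.607, 0.368, 0.135, 0.050. The SD of absolute change is 10 × √(2 × mean/10) = 10.0, 14.1, 20.0, 24.5.

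The direction of the false signal depends on the assumed level. When many entry counts are 0, those patients drop out. The remainder are those who were higher at entry and tend to fall, so the mean is negative. At mean counts of 20 and 30 the small denominators dominate and the mean is positive. Where zeros are reported as <10, nothing is undefined and the median is 0, but the mean and SD remain unstable.

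**Step 4: the same statistic in predecessor-placebo patients.** Assumed log-normal entry counts with median 200, 300 or 400 and log-SD 0.7; mean 10 after dosing. None is undefined. Mean percent change is −94%, −96% and −97%, with SD 10, 6 and 5 points.

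**Step 5: a pre-benralizumab reference for continuing patients.** With an assumed reference of 300, later counts of 0, 10, 20 and 30 give −100%, −97%, −93% and −90%. With an entry count of 10, the same later counts give −100%, 0%, +100% and +200%.

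**The case against.** The strongest reply is that the plan already answers the objective. It concerns eosinophil levels, and SAP 4.2.5.2 gives absolute counts at every visit in all four groups, with means, medians and ranges under SAP 4.1. The predecessor-placebo groups are reported separately, from a baseline before any benralizumab, and show each regimen's effect directly. The BORA-entry baseline is also a deliberate choice, stated in both documents, and near-zero change from it is what maintenance should look like.

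Most of this stands. A reader might infer that the plan cannot show the regimens' impact on eosinophils, or that absolute change from BORA entry is as uninformative as percent change. The documents support neither. Absolute change is defined whenever both values exist; it shows maintenance during treatment and recovery afterwards (+190 in Step 2). A reader might also take percent change to be undefined for any very low baseline. Under SAP 3.1.2 a less-than result is analysed as its number, so only a recorded exact 0 has that effect, and the documents do not say how the laboratory reports low counts.

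Two further replies have force. The size of the problem rests on assumed counts. A second reference point also has a price: the continuing groups' figure would largely reflect the predecessor study, with longer exposure and in patients who completed that study.

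What the reply does not reach is percent change itself. SAP 4.2.5.2 already provides the counts and their changes from baseline, so the new statistic in 4.2.6.3 is percent change. That is the one that fails in two of the four groups.

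**Conclusion.** The point holds for one statistic in two groups. For patients continuing Q4W or Q8W from the predecessor study, percent change in eosinophils from BORA entry has an on-treatment denominator. It is unstable, has no value at a recorded baseline of 0, and measures neither depletion from the pre-benralizumab level nor recovery towards it.

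That the denominator is on-treatment follows from the documents. That it is low is what protocol 1.2 leads one to expect. How low is not given, so the figures above (5% to 61% undefined, false mean changes of −56% to +30%) illustrate the range under the stated assumptions and do not predict the trial's results.

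Absolute counts, absolute change from BORA entry and the predecessor-placebo columns are sound. The study is descriptive (SAP 1.3 and 4.1) and no test is affected. Severity is minor, but the correction is cheap and prevents a misleading table.

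**What to change.** In SAP 4.2.6.3:

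- For predecessor-benralizumab patients, replace percent change from BORA entry with change and percent change from the predecessor baseline count. State that this is the last count before the first predecessor dose, since these documents do not define it. Footnote it as a different reference point with longer exposure.
- For the same patients, keep absolute counts by visit and absolute change from BORA entry for the maintenance question.
- For predecessor-placebo patients, keep the BORA baseline, which also precedes any benralizumab.

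The cost is a change of wording and one merge of a variable that the SAP already uses: for the 300/µL split of SIROCCO and CALIMA data in 4.2.6, and for the disposition and baseline summaries in 4.2.1 and 4.2.2. The downside is two labelled reference points in the eosinophil tables, which the footnote has to make plain.

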4.2.7 Analysis methods for patient-reported outcomes

All PROs data from SIROCCO and CALIMA will be summarized by treatment for the patients with predecessor baseline blood eosinophil count $\geq 300/\mu\text{L}$ and $< 300/\mu\text{L}$. PROs data from ZONDA will be summarised for the FAS regardless of predecessor baseline eosinophil counts.

4.2.7.1 ACQ-6

The following summaries will be presented by treatment.

- Descriptive summaries on the mean score values and changes from baseline to each post-baseline visit
- Number and percentage of patients in each asthma control status (well controlled, partly controlled, and not controlled) at each visit
- Number and percentage of patients in each asthma control status (well controlled, partly controlled, and not controlled) at each post-baseline visit by baseline control status
- Number and percentage of patients in each asthma responder status (Improved, No change, Deterioration) from baseline to each post-baseline visit
- Number and percentage of patients in each asthma responder status (Improved, No change, Deterioration) at each post-baseline visit by baseline asthma control status (well controlled, partly controlled, and not controlled)

4.2.7.2 AQLQ(S)+12

The following summaries will be presented by treatment group.

- Overall score and 4 domain scores and change from baseline to each post-baseline visit
- HRQoL responder status (Improved, No change, Deterioration) from baseline to each post-baseline visit

4.2.7.3 WPAI+CIQ

The WPAI+CIQ are collected at baseline and Follow-up visit for adults, and baseline and EOT visit for adolescents. The following summaries will be presented by treatment group.

- Number and percentage of patients employed and attending classes
- Number of work hours missed and the number of class hours missed due to asthma
- Summary scores of absenteeism, presenteeism, absenteeism + presenteeism combined (ie work/class productivity loss),
- Activity impairment

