3.7 Withdrawal from the study

3.7.1 Withdrawal of Informed Consent

Patients are free to withdraw from the study at any time (IP and assessments) without prejudice to further treatment. Patients who discontinue IP will be discontinued from the study.

A patient who withdraws consent will always be asked about the reason(s) and the presence of any adverse events (AE). The Investigator will follow up AEs outside of the clinical study. The enrolment/randomization code of the withdrawn patient cannot be reused.

If patient agrees, he/she will be asked to return to the study center and complete procedures described for the IPD and FU visits within 4 weeks (+7 days) and 16 weeks (\pm 7 days) after the last dose of IP, respectively.

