8.4.3.3 Health Care Utilization and Work Productivity and Activity Impairment

The ten questions included in the WPAI+CIQ are as follows:

- 1 = currently employed (yes/no)
- 2 = hours missed work due to health problems
- 3 = hours missed work due to other reasons
- 4 = hours actually worked
- 5 = degree health affected productivity while working (0-10 scale, with 0 meaning no effect)
- 6 = attends class in an academic setting (yes/no)

7 = hours missed class due to health problems

8 = hours actually attended class

9 = degree health affected productivity while attending class (0-10 scale, with 0 meaning no effect)

10 = degree health affected regular activities (other than work or class) (0-10 scale, with 0 meaning no effect)

For the work related questions, the following calculations should be used to create the variables of interest:

- Number of work hours missed = Q2
- Absenteeism = $Q2/(Q2+Q4)$
- Presenteeism = $Q5/10$
- Work Productivity Loss = $Q2/(Q2+Q4)+[(1-Q2/(Q2+Q4))x(Q5/10)]$
- Activity Impairment = $Q10/10$

For the class-related questions, the following calculations should be used to create the variables of interest:

- Number of class hours missed = Q7
- Absenteeism = $Q7/(Q7+Q8)$
- Presenteeism = $Q9/10$
- Absenteeism+Presenteeism = $Q7/(Q7+Q8)+[(1-Q7/(Q7+Q8))x(Q9/10)]$
- Activity Impairment = $Q10/10$

The primary outcome for those not previously treated with benralizumab in the predecessor study will be reductions in the variables of interest described above (number of work/class hours missed, absenteeism, presenteeism, and work productivity loss and activity impairment) when comparing the values at the EOT to baseline (Visit 1). The primary outcome for those previously treated with benralizumab in the predecessor study will be no change in the variables of interest when comparing values at the EOT visit to baseline (Visit 1).

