The mean rates of healthcare utilization by type of event (in-patient hospitalizations, emergency department visits/urgent care visits combined, unscheduled outpatient visits, and all unscheduled healthcare encounters) will be summarized over the treatment period. The primary outcome for those previously treated with benralizumab in the predecessor study will be no change in the mean rate of healthcare encounters by type in this safety extension study compared with the mean rates of healthcare encounters by type among the benralizumab treated patients in the predecessor studies. The primary outcome for those not previously treated with benralizumab in the predecessor study will be mean rates of healthcare encounters by type comparable to the mean rates of healthcare encounters for those previously treated with benralizumab in the predecessor study.

The number and percentage of patients employed and attending classes will be summarized for Visit 1 and the EOT visit. The number of work hours missed and the number of class hours missed due to asthma as well as the 4 summary scores of absenteeism, presenteeism, absenteeism + presenteeism combined, and activity impairment will also be summarized for Visit 1 and the EOT visit. The primary outcome for those not previously treated with benralizumab in the predecessor study will be reductions in the variables of interest (number of work/class hours missed, absenteeism, presenteeism, and work productivity loss and activity impairment) when comparing the values at the EOT to baseline (Visit 1). The primary outcome for those previously treated with benralizumab in the predecessor study will be no change in the variables of interest when comparing values at the EOT visit to baseline (Visit 1).

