3.3.3 Work Productivity and Activity Impairment (WPAI+CIQ)

The 10 questions included in the WPAI+CIQ are as follows:

- 1 = currently employed (yes/no)
- 2 = hours missed work due to health problems
- 3 = hours missed work due to other reasons
- 4 = hours actually worked
- 5 = degree health affected productivity while working (0-10 scale, with 0 meaning no effect)
- 6 = attends class in an academic setting (yes/no)
- 7 = hours missed class due to health problems
- 8 = hours actually attended class
- 9 = degree health affected productivity while attending class (0-10 scale, with 0 meaning no effect)
- 10 = degree health affected regular activities (other than work or class) (0-10 scale, with 0 meaning no effect)

If the answer to question 1 is 'No, not currently employed', then the patient should skip to question 6. If the answer to question 6 is 'No, not currently attending class', then the patient should skip to question 10.

The WPAI+CIQ provides 4 types of scores: absenteeism (work or class time missed), presenteeism (impairment at work or class/reduced on-the-job effectiveness), work productivity loss (overall work or class impairment/absenteeism plus presenteeism), and activity impairment. WPAI+CIQ outcomes are expressed as impairment percentages, with higher numbers indicating greater impairment and less productivity.

For the work related questions, the following calculations should be used to create the variables of interest:

- Number of work hours missed = Q2
- Absenteeism = $Q2/(Q2+Q4)$
- Presenteeism = $Q5/10$
- Work Productivity Loss = $Q2/(Q2+Q4)+[(1-Q2/(Q2+Q4))x(Q5/10)]$
- Activity Impairment = $Q10/10$

For the class-related questions, the following calculations should be used to create the variables of interest:

- Number of class hours missed = Q7
- Absenteeism = $Q7/(Q7+Q8)$
- Presenteeism = $Q9/10$

- Class Productivity Loss = $Q7/(Q7+Q8)+[(1-Q7/(Q7+Q8))x(Q9/10)]$
- Activity Impairment = $Q10/10$.

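### SAP 4.2.7.3 plans WPAI+CIQ levels but no within-patient change, so the baseline and later work and class summaries cover overlapping but different patients and can differ when no patient has changed

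*SAP*

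**What the plan says.** **Outcome.** For former placebo patients, Protocol 8.5.1.4 looks for "reductions in the variables of interest (number of work/class hours missed, absenteeism, presenteeism, and work productivity loss and activity impairment"; Protocol 8.4.3.3 says this is judged "when comparing the values at the EOT to baseline (Visit 1". For patients already on benralizumab, the outcome is no change over the same interval. On method, Protocol 8.5.1.4 says the scores "will also be summarized for Visit 1 and the EOT visit".

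**Planned output.** SAP 4.2.7.3 lists four items by treatment group: numbers employed and attending class, hours missed, "Summary scores of absenteeism, presenteeism, absenteeism + presenteeism combined (ie work/class productivity loss", and activity impairment. None is a change from baseline. The SAP does name change from baseline for ACQ-6 (4.2.7.1), AQLQ(S)+12 (4.2.7.2), the EQ-5D visual analogue scale (4.2.7.4) and FEV1 (4.2.6.2). SAP 2.4 defines change in general as later value minus baseline value, missing if either is missing.

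**Who has a score.** Under SAP 3.3.3, if a patient is not employed, "then the patient should skip to question 6"; a patient not attending class goes on to question 10. Question 10 itself ("10 = degree health affected regular activities (other than work or class") is not skipped by either route.

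**Timing.** SAP 4.2.7.3 states: "The WPAI+CIQ are collected at baseline and Follow-up visit for adults, and baseline and EOT visit for adolescents". Protocol 5.3.2.3 and 8.5.1.4 place the later assessment at EOT for everyone. SAP section 6 declares no change from the protocol.

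**The concern.** The protocol's outcome is a statement about change, but the listed output is two sets of levels. A reader will subtract one from the other. For the work and class scores, that subtraction mixes within-patient change with change in who is being scored. A patient who loses work between the visits counts in the baseline mean and not in the later one; a patient who starts work does the reverse. The same applies to class attendance, which adolescents may well finish before Week 108.

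If those who leave are more impaired than those who stay, the later mean falls. That resembles the reduction looked for in former placebo patients and could mask worsening in continuing patients. If they are less impaired, it rises. Every BORA group receives benralizumab, so there is no untreated group against which to notice such a shift.

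**Working it through.** **1. Which variables depend on what (SAP 3.3.3).**

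| Variable | Scored at a visit if | Why the two sets can differ |
|---|---|---|
| Work hours missed, absenteeism, presenteeism, productivity loss | employed then | work lost or gained; missing assessment |
| Class equivalents | attending class then | class left or started; missing assessment |
| Activity impairment (Q10) | Q10 answered | missing assessment only |

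The hybrid LOCF in SAP 3.3.1 and 3.3.2 covers ACQ-6 and AQLQ(S)+12 only, so a missing later WPAI+CIQ score stays missing.

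**2. Leavers only.** The plan states no WPAI+CIQ figure to reproduce. Let f be the share of baseline scorers with no later score, L the leavers' mean baseline score and S the stayers'. Suppose nobody changes.

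- Baseline mean = (1 - f)S + fL
- Later mean = S
- Apparent change = S - [(1 - f)S + fL] = -f(L - S)

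Values of f and L - S are assumptions. Apparent change in points (0-100 scale):

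| f | L - S = 10 | 20 | 30 |
|---|---|---|---|
| 5% | -0.5 | -1.0 | -1.5 |
| 10% | -1.0 | -2.0 | -3.0 |
| 20% | -2.0 | -4.0 | -6.0 |
| 30% | -3.0 | -6.0 | -9.0 |

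With L = S the shift is 0. With f = 20% and leavers 10 points *below* stayers, it is -0.20 × (-10) = +2.0.

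**3. Adding entrants.** If a share e of later scorers is new, with mean N, the later mean is (1 - e)S + eN. Take S = 20, L = 40, f = 20%, e = 5%.

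- Baseline mean = 0.8 × 20 + 0.2 × 40 = 24.0
- N = 10: later mean = 0.95 × 20 + 0.05 × 10 = 19.5, apparent change -4.5
- N = 30: later mean = 0.95 × 20 + 0.05 × 30 = 20.5, apparent change -3.5

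**4. Simulation.** Each patient's score was held fixed, with an assumed mean of 25. The chance of having no later score was either unrelated to the score or rising with it.

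| Loss | Leavers minus stayers | Apparent change |
|---|---|---|
| 12.0% | 0.0 | 0.0 |
| 12.5% | 8.2 | -1.0 |
| 14.3% | 16.8 | -2.4 |

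**5. Paired change.** Applying the SAP 2.4 definition to patients with both scores gives exactly 0 in every scenario above, because no patient changed. In step 3 the paired baseline mean would be 20, not 24.

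**The case against.** **The SAP does not forbid a change summary.** This is fair. SAP 4.2.7.3 names variables without excluding change, and SAP 2.4 already holds the paired formula. The by-visit wording is the protocol's. But SAP 2.4 says how a change is computed, not that it is produced for this instrument, and nothing limits the level summaries to patients with both values. Where the SAP wants change for a questionnaire, it says so.

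**Stopping treatment does not by itself remove the later score.** A reader might infer that it does from Protocol 3.7.1: "Patients who discontinue IP will be discontinued from the study". The documents do not support that. Protocol 3.6 and 4.2.3.4 still ask such patients to attend the IPD and Follow-up visits, 3.7.1 asks the same of patients who withdraw consent, if they agree, and SAP 4.1 keeps data regardless of premature discontinuation. If the adult assessment is at Follow-up, these patients can contribute. If it is at EOT, SAP 2.3 uses the visit as recorded for WPAI+CIQ, and nothing maps an IPD score to EOT. Attrition therefore hinges partly on the unresolved time point. Patients who roll over to MELTEMI do not add to it, since SAP 2.1 summarises them separately.

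**The planned counts of employed patients already show shifts.** They show the net shift, not who left or joined.

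**Pairing is selective too.** This stands. Patients employed at both visits exclude anyone who lost work through asthma, so a paired mean alone still hides that deterioration. A transition table is needed beside it.

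**The stakes are low.** Agreed: SAP 1.3 says the study is not powered for any hypothesis test, and WPAI+CIQ is one of several secondary endpoints.

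**Conclusion.** The mismatch is real. The protocol's WPAI+CIQ outcome is change against Visit 1, the SAP lists levels only, and for work and class scores the levels at the two visits come from overlapping but different patients. Their difference can therefore depart from zero when nobody has changed.

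The size cannot be derived from the documents. The figures of -0.5 to -9.0 points rest on assumed loss and an assumed gap between leavers and stayers. The bias vanishes if loss is unrelated to the score, and it reverses if leavers are less impaired.

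A reader might infer that the plan will manufacture a benefit. The documents do not support this, because nothing in them fixes the direction or shows how many patients change status. A reader might also take every WPAI+CIQ variable to be affected alike. Activity impairment does not depend on work or class status and is exposed only to missing later assessments.

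The point is a worthwhile, inexpensive improvement to a descriptive secondary endpoint. No safety conclusion turns on it.

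**What to change.** 1. Reconcile the adult post-baseline time point first. SAP 4.2.7.3 says Follow-up (Week 68); Protocol 5.3.2.3 and 8.5.1.4 say EOT (Week 56), 12 weeks earlier. Check both against the protocol's assessment schedules, and record any departure in SAP section 6. State how a WPAI+CIQ form completed at an IPD visit is used, if there is one.
2. Add to SAP 4.2.7.3 the change from baseline, as defined in SAP 2.4, in patients with a score at both visits. For work and class scores this means employed, or attending class, at both; for activity impairment it means all patients with both values. Report the paired n and the baseline mean in that same set.
3. Add a baseline-by-later-visit table of employed / not employed / missing, and the same for class, so that loss of work is visible.
4. Keep the by-visit summaries as supportive.

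The cost is SAP wording and one or two extra tables, with no new data collection. The downside is smaller paired sets, most noticeably once SIROCCO and CALIMA patients are split by baseline eosinophil count under SAP 4.2.7.
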